14.3 Late Clinical Failure (LCF)

LCF is defined as meeting any of the following:

- a) Danger signs or severe malaria in the presence of parasitemia on any day between 4 and 28 days after treatment (i.e., between Days 5 and 29) in participants who did not previously meet any of the criteria of ETF.
- b) Presence of parasitemia on any day between 4 and 28 days after treatment with temperature $\geq 37.5^{\circ}\text{C}$ in participants who did not previously meet any of the criteria of ETF.

The same ICEs and strategies as defined for ACPR (see Section 14.1) will be applied for LCF, however, limited to events that occur between 4 and 28 days after treatment (i.e., between Days 5 and 29). Failure is considered presence of LCF.

The same analyses and population-level summaries as described for ETF will be applied for LCF.

14.4 Late Parasitological Failure (LPF)

LPF is defined as presence of parasitemia on any day between 7 and 28 days after treatment (i.e., between Days 8 and 29) with temperature $< 37.5^{\circ}\text{C}$ in participants who did not previously meet any of the criteria of ETF or LCF.

The same ICE and strategies as defined for ACPR (see Section 14.1) will be applied for LPF, however, limited to events that occur between 7 and 28 days after treatment (i.e., between Days 8 and 29). Failure is considered presence of LPF.

The same analyses and population-level summaries as described for ETF will be applied for LPF.

14.5 Fever clearance time

Fever clearance time is defined as the time (in hours) from first dosing to the first measurement of temperature $< 37.5^{\circ}\text{C}$ for 2 consecutive temperature readings, plus confirmed normal temperature ($< 37.5^{\circ}\text{C}$) 24 hours after the first normal body temperature reading. Participants who are initially included on documented history of fever and who do not subsequently have a documented temperature reading of $> 37.5^{\circ}\text{C}$ at the pre-dose visit or during the 24 hours following initial dosing will not be considered for the population-level summary.

For fever clearance time, the ICEs as defined by the study protocol will be identified and handled as described in the following:

- **Intake of rescue medication:** See Section 14.1 for description of rescue medication. A composite variable strategy is applied, i.e., time to fever clearance is censored at the time of rescue medication intake. In order to qualify as ICE, the intake of rescue medication has to take place within the first 3 days after treatment initiation.
- **Intake of concomitant medications as a continuous treatment that have an impact on fever:** Filtering concomitant medications programmatically for paracetamol, acetaminophen, NSAIDs (ibuprofen, naproxen), salicylic acid, and by medical review. A composite variable strategy is applied, i.e., time to fever clearance is censored at the time of first concomitant medication intake. In order to qualify as ICE, the start date of intake of concomitant medication has to take place within the first 3 days after treatment initiation. If the fever medication was taken prior to dosing, participants will still be included for analysis. Strategies for intercurrent events will not apply.
- **Intake of prohibited medication that impacts treatment effect (e.g., drug with antimalarial activity):** Filtering concomitant medications programmatically for sulphadoxine-trimethoprim, doxycycline, quinolone antibiotics including fluoroquinolones, azithromycin, erythromycin and all other macrolides and by medical review. A composite variable strategy is applied, i.e., time to fever clearance is censored at the time of prohibited medication intake. In order to qualify as ICE, the intake of prohibited medication has to take place within the first 3 days after treatment initiation.
- **Experience of any event that affects absorption (i.e., vomiting within the study intervention absorptive period of $2 \times \text{median } t_{\text{max}}$) or immune response (severe immunocompromised participants):** See Section 14.1 for description of events affecting absorption or immune response. A treatment policy strategy is applied, i.e., treatment effect is estimated regardless of intercurrent event.
- **Premature study discontinuation due to lack of efficacy:** See Section 14.1 for description of ICE. An on-treatment strategy is applied, i.e., time to fever clearance is censored at the day of the last available body temperature assessment. Note: If premature study discontinuation occurs after fever clearance has already been observed, then the strategy will not be applied.
- **Death due to malaria:** See Section 14.1 for description of death due to malaria. An on-treatment strategy is applied, i.e., time to fever clearance is censored at the day of the last available body temperature assessment. Note: If death occurs after fever clearance has already been observed, then the strategy will not be applied.

Median fever clearance time and 95% CIs will be estimated by use of the Kaplan-Meier method. Confidence intervals will be calculated using log-log transformation. Participants with no fever clearance or ICEs will be censored at the day of the last temperature assessment. Kaplan-Meier plots including a table with number of participants at risk and number of events will be provided. To explore whether there is an impact of dose group (Part A vs. Part B Cohort B0), age (continuous), sex, and parasite density at baseline on time to fever clearance, a Cox Proportional Hazards model will be applied.

[figure not shown]

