#### 5.1 Inclusion Criteria

Participants are eligible to be included in the study only if all the following criteria apply:

Category	Criterion
Age:	1. Are $\geq 12$ and $\leq 55$ years of age ( $\geq 18$ and $\leq 55$ years of age for Part A) at the time of signing the informed consent.
Type of Participant and Disease Characteristics:	2. Microscopic confirmation of acute uncomplicated P. falciparum using Giemsa-stained thick and thin film. 3. P. falciparum parasitemia of $\geq 1,000$ to $\leq 50,000$ asexual parasites/ $\mu$ L of blood in Part A and P. falciparum parasitemia of $> 1,000$ to $\leq 150,000$ asexual parasites/ $\mu$ L of blood in Part B. 4. Axillary temperature $\geq 37.5^{\circ}\text{C}$ or tympanic temperature $\geq 38.0^{\circ}\text{C}$ (use as per COVID-19 protocols at the site [only at Screening]), or history of fever during the previous 24 hours (at least documented verbally).
Weight:	5. Have a body weight $\geq 24$ kg.

Category	Criterion

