2.0	21OCT2024	PPD	Updates in Section 7 and 14.5 to include only participants who had a temperature $>37.5^{\circ}\text{C}$ at the pre-dose visit or during the 24 hours following dosing will be included. If the fever medication was taken prior to dosing, participants will still be included for analysis. Strategies for intercurrent events will not apply.

4 Purpose of the Integrated Analysis Plan

The purpose of this Integrated Analysis Plan (IAP) is to document technical and detailed specifications for the primary, secondary and **CCI** analyses of data collected for protocol MS201618_0033. Results of the analyses described in this IAP will be included in the Clinical Study Report (CSR). Additionally, the planned analyses identified in this IAP may be included in regulatory submissions or future manuscripts. Any post-hoc, or unplanned analyses performed to provide results for inclusion in the CSR but not identified in this prospective IAP will be clearly identified in the CSR.

The IAP is based on the study protocol and protocol amendments and is prepared in compliance with ICH E9. It describes analyses planned in the protocol version 3.0 with changes documented in section 7 below. The IAP may be updated as a result of protocol amendments, clarifications, or corrections. The IAP will not be updated with every protocol amendment unless protocol changes affect data analyses described in this IAP. Any updates to the IAP prior to data review will be documented in the modification history above and will be reviewed and approved accordingly. Any changes to the described analysis occurring after data review will be labeled as such and documented in the CSR.

The wording used in this IAP is chosen to best match the respective wording in the study protocol template, the CSR template, CDISC requirements and special requirements for table layouts. Therefore, the following approach is used:

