	
Endpoint: Fever clearance time defined as the time from first dosing to the first measurement of temperature $< 37.5^{\circ}\text{C}$ for 2 consecutive temperature readings plus confirmed normal temperature 24 h after the first normal body temperature reading.
 
Target Population: Adult patients with acute uncomplicated malaria due to P. falciparum with an increased temperature ($\geq 37.5^{\circ}\text{C}$)
 
Treatment: see endpoint 3
 
Intercurrent Event Strategy:
 
• Intake of rescue medication within 3 days after treatment initiation: Composite variable strategy, i.e., time to fever clearance is censored at time of rescue medication intake.• Intake of concomitant medications as a continuous treatment that have an impact on fever within 3 days after treatment initiation: Composite variable strategy, i.e., time to fever clearance is censored at time of concomitant medication intake.• Intake of prohibited medication that impacts treatment effect (e.g., drug with antimalarial activity) within 3 days after treatment initiation: Composite variable strategy, i.e., time to fever clearance is censored at time of prohibited medication intake.• Experience of any event that affects absorption (i.e., vomiting within the study intervention absorptive period of $2 \times$ median t_{max}) or immune response (severe immunocompromised participants): Treatment policy strategy, i.e., treatment effect is estimated regardless of intercurrent event or Principal Stratum strategy• Premature study discontinuation due to lack of efficacy: On-treatment strategy, i.e., time to fever clearance is censored at the day of the last available body temperature assessment• Death due to malaria: On-treatment strategy, i.e., time to fever clearance is censored at the day of the last available body temperature assessment 
Population-level Summary: Median fever clearance time as estimated by Kaplan-Meier method
	11
	
Endpoint: Parasite clearance time defined as time from dosing to the first negative (no parasites) film (microscopy)
 
Target Population: see endpoint 3
 
Treatment: see endpoint 3
 
Intercurrent Event Strategy: see previous endpoint with the exception of intake of concomitant medications, which is not an ICE for parasite clearance time.
	12

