- For Estimands #11, 12, 28, and 29, the ICE was changed. Time to fever clearance and time to parasite clearance will be censored at the time of intake of rescue/fever/prohibited medications that are taken within 3 days after treatment initiation.
- For Estimands #11 and 28 (analysis of fever clearance), only participants who had a temperature $>37.5^{\circ}\text{C}$ at the pre-dose visit or during the 24 hours following dosing will be included. If the fever medication was taken prior to dosing, participants will still be included for analysis. Strategies for intercurrent events will not apply.

- Analysis of Estimands #8, 9, 25, and 26, crude and PCR-adjusted efficacy 8 days after treatment, will not be conducted as no new information would be added.
- CCI
[REDACTED]
[REDACTED]
[REDACTED]
- Analysis of Estimands #13, 14, 15, 30, 31, and 32, time to recrudescence, re-infection, and re-emergence, will not be conducted as no new information would be added.
- For any analysis using axillary temperature, the temperature measured at other locations will be used instead without adjustment if the axillary temperature is not collected. The number of participants or visits with temperature measured at different body locations will be described in the footnote of the output.

8 Analysis Sets

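### SAP 7 and SAP 14.5 select different participants for fever clearance time, and neither matches the target population in SAP 5

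*SAP*

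**What the plan says.** - **SAP 5, endpoints 11 (Part A) and 28 (Cohort B0).** The target population is patients "with an increased temperature", given as 37.5 °C or more. No time window is named and entry route plays no part.
- **SAP 7.** For the same two estimands, only those with a temperature above 37.5 °C "at the pre-dose visit or during the 24 hours following dosing will be included". Entry route is not mentioned, so the rule covers everyone.
- **SAP 14.5.** The exclusion concerns "Participants who are initially included on documented history of fever and who do not subsequently have a documented temperature reading of" above 37.5 °C "at the pre-dose visit or during the 24 hours following initial dosing will not be considered for the population-level summary". No condition is placed on participants who entered with a measured fever.
- **SAP 3, entry for version 2.0.** It records "Updates in Section 7 and 14.5 to include only participants who had a temperature" above 37.5 °C in that window, so both sections were meant to carry one rule.
- **Protocol 8.1, secondary endpoints.** This is the source of the 14.5 sentence: the same history-only exclusion, with a window of 24 hours after dosing and no mention of pre-dose.

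Clearance in 14.5 requires two consecutive readings below 37.5 °C plus a normal reading 24 hours after the first. The summary is a Kaplan-Meier median with 95% CI, with an exploratory Cox model that includes dose group.

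**The concern.** The analysis set should follow from the SAP without choice. Here, two programmers working from different sections could build different sets. The participant who separates them is one with fever at Screening and none from pre-dose onward. Keeping that person adds an early event that says little about treatment, because the fever had gone before the first dose. Enough such people would shorten the median.

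The threshold is a second, separate mismatch. The SAP treats 37.5 °C or more as fever in the estimand, and also in the early treatment failure and late clinical failure definitions. It treats less than 37.5 °C as normal for clearance. Only entry to the fever analysis uses above 37.5 °C. A reading of exactly 37.5 °C is therefore neither normal for the endpoint nor fever for entry to it.

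**Working it through.** **Step 1. Can the separating participant occur?** Protocol 5.1, criterion 4, admits on a measured temperature at Screening (axillary 37.5 °C or more, or tympanic 38.0 °C or more) or on a history of fever in the previous 24 hours. Protocol Table 1 allows up to 12 hours from diagnosis to dosing, with 6 hours as the norm. Paracetamol for fever is permitted (protocol 6.8). Under SAP 14.5, fever medication taken before dosing neither excludes a participant nor triggers the intercurrent-event strategy. So a screening fever can be gone by pre-dose. The first post-dose time in the temperature row of protocol Table 2 is 6 hours.

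**Step 2. Apply the three rules.** Peak means the highest reading from pre-dose to 24 hours.

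| Participant | SAP 5 | SAP 7 | SAP 14.5 |
|---|---|---|---|
| Any entry route, peak 38.5 | in | in | in |
| History entrant, peak 37.2 | out | out | out |
| History entrant, peak exactly 37.5 | in | out | out |
| Measured-fever entrant, peak exactly 37.5 | in | out | in |
| Measured fever at Screening (e.g. 38.2), peak 37.2 | undetermined (no window) | out | in |

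SAP 7 and 14.5 differ in the last two rows. SAP 5 differs from SAP 7 in the third and fourth rows, and from 14.5 in the third.

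**Step 3. Effect of early clearers on the median (illustration).** The plan gives no figure to reproduce. Take 15 invented times in hours: 6, 12, 12, 18, 18, 18, 24, 24, 24, 30, 30, 36, 36, 42, 48. The 8th is the median, 24. Add k participants at 6 h:

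- k = 1: 16 values, 8th and 9th are 24 and 24, median 24.
- k = 2: 17 values, 9th is 24, median 24.
- k = 3: 18 values, 9th and 10th are 18 and 24, median (18 + 24)/2 = 21.
- k = 5: 20 values, 10th and 11th are 18 and 18, median 18.

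So three of 18 (17%) or five of 20 (25%) would have to be of this type.

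**Step 4. The same by simulation.** Assumptions: m participants febrile under SAP 7; exponential clearance times with true median 12 or 24 h, rounded up to a 6-hour grid and capped at 72 h; no censoring; median taken as the lower middle value. Entries are the average median before → after adding k clearers at 6 h, with the share of runs in which it changed.

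| m | k | true median 12 h | true median 24 h |
|---|---|---|---|
| 8 | 2 | 14.0 → 10.5 (48%) | 24.9 → 18.0 (67%) |
| 16 | 2 | 14.5 → 12.5 (30%) | 26.0 → 22.1 (51%) |
| 24 | 2 | 14.6 → 13.4 (21%) | 26.3 → 23.7 (40%) |
| 8 | 4 | 14.0 → 7.9 (72%) | 24.9 → 12.3 (91%) |
| 16 | 4 | 14.5 → 10.8 (56%) | 25.9 → 18.6 (79%) |
| 24 | 4 | 14.7 → 12.2 (40%) | 26.3 → 21.1 (68%) |

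With k = 1 the median never moved, but that follows from even m and the lower-middle convention. Averaging the two middle values could give a small shift.

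**Step 5. How many might peak at exactly 37.5 °C?** This needs assumptions that the documents do not supply. With peaks normal and recorded to 0.1 °C, the probability of 37.45 to 37.55 is 5.2% (mean 37.8, SD 0.7), 4.1% (38.0, 0.8) or 3.0% (38.3, 0.9). For the 25 planned in Cohort B0 that is 25 × 0.030 to 25 × 0.052, or 0.75 to 1.3 participants. Deleting any one value from the 15 in Step 3 leaves the median at 24.

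**The case against.** The strongest reply is that the intended rule is known. SAP 4 says changes from the protocol are documented in Section 7, and the version 2.0 entry says 7 and 14.5 were both updated to the same restriction. On that view SAP 5 only describes a population, and 14.5 is one incompletely edited sentence. This stands as evidence of intent, and the proposed fix relies on it. It does not remove the conflict, which lies between two current sections. The operative sentence in 14.5 still says something else, and no order of precedence is given. SAP 5 is not simply carried-over protocol text either, since its censoring rules were rewritten for the SAP.

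The separating profile is also narrow. Dosing is normally within 6 hours of diagnosis, and continuous fever medication started within 3 days of treatment initiation is censored at first intake under 14.5. Some of these participants would therefore be censored rather than counted as cleared. That stands.

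A reader might go further and infer that the reported median, or the Part A versus Cohort B0 comparison in the Cox model, will be wrong. The documents do not support that. They give no counts of either type of participant. Any distortion of the dose-group effect depends on how such participants fall between the two groups, and the model is exploratory. A reader might also infer that everyone peaking at exactly 37.5 °C is lost whichever section is followed. Under 14.5 a measured-fever entrant stays in, and is uncleared only at that reading.

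**Conclusion.** The inconsistency is real and worth correcting. SAP 7 and 14.5 define different analysis sets, and the entry threshold in both disagrees with the estimand in SAP 5 and with the clearance limit. Its size is conditional. One or two affected participants need not move the median, although in the simulated examples two changed it in 21% to 67% of runs. Several could shorten it noticeably, since the cohorts are small (12 and 25 planned, reported separately) and only their febrile members count. The threshold mismatch alone, at about one participant in Cohort B0 under the assumed distributions, would probably not matter numerically. All these sizes rest on invented or assumed data. Fever clearance is a secondary, descriptive endpoint, and the primary analysis of PCR-adjusted ACPR in Cohort B0 is untouched.

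**What to change.** 1. In SAP 14.5, delete the restriction to participants who entered on a documented history of fever, so that the SAP 7 rule applies to all entry routes.
2. State one threshold and one window in identical words in SAP 5 (endpoints 11 and 28), 7 and 14.5: at least one reading of 37.5 °C or more at pre-dose or in the 24 hours after dosing. This threshold agrees with the estimand and with clearance at less than 37.5 °C.
3. List the threshold in SAP 7 as a change from protocol 8.1, which uses above 37.5 °C.
4. If data review has already taken place, label the change and document it in the CSR, as SAP 4 requires.

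The cost is a few lines of SAP text and one analysis flag. No new data are needed.

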### Assessment of Secondary Efficacy Endpoints

For the definitions of secondary efficacy endpoints please refer to [Table 3](#).

Recrudescence is defined as reappearance of parasites of the same isolate as initial infection, with or without clinical signs, after initial clearance of parasites from the peripheral blood, with positive blood smear and PCR genotyping confirmation of the same isolate.

The time to fever clearance is defined as the time from first dosing to the first normal reading of temperature ( $< 37.5^{\circ}\text{C}$ ) for 2 consecutive normal temperature readings plus confirmed normal temperature 24 hours after the first normal body temperature reading. The method of temperature measurement must be the same (axillary) for all measures in the same patient. Those participants who are initially included on documented history of fever and who do not subsequently have a documented temperature reading of  $> 37.5^{\circ}\text{C}$  during the 24 hours following initial dosing, will not be included in this endpoint analysis.

The parasite clearance time represents the time from first dosing to time of first blood draw with parasite clearance. Parasite clearance is defined as zero presence of parasites for 2 consecutive negative readings at least 6 hours apart.

The PRR index is defined as  $\frac{C_{48}}{C_0} - 1$ , where  $C_{48}$  is the parasite count at 48 hour and  $C_0$  is the count at pre-dose on Day 1 (Baseline).

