To describe the clinical and parasitological efficacy of the M5717-pyronaridine combination in adult and adolescent participants with acute uncomplicated malaria due to P. falciparum	
Endpoint: ETF
 
Target Population: See endpoint 19
 
Treatment: see endpoint 19
 
Intercurrent Event Strategy: See endpoint 3
 
Population-level Summary: See endpoint 3
	20
	
Endpoint: LCF
 
Target Population: See endpoint 19
 
Treatment: see endpoint 19
 
Intercurrent Event Strategy: See endpoint 4
 
Population-level Summary: See endpoint 4
	21
	
Endpoint: LPF
 
Target Population: See endpoint 19
 
Treatment: see endpoint 19
 
Intercurrent Event Strategy: See endpoint 5
 
Population-level Summary: See endpoint 5
	22
	
Endpoint: Crude (PCR-uncorrected) ACPR 28 and 42 days after treatment
 
Target Population: See endpoint 19
 
Treatment: see endpoint 19
 
Intercurrent Event Strategy: See endpoint 6
 
Population-level Summary: See endpoint 6
	23
	
Endpoint: PCR-adjusted ACPR 42 days after treatment
 
Target Population: See endpoint 19
	24

	
Treatment: see endpoint 19
 
Intercurrent Event Strategy: See endpoint 7
 
Population-level Summary: See endpoint 7
	
	
Endpoint: Fever clearance time
 
Target Population: Adult and adolescent patients with acute uncomplicated malaria due to P. falciparum with an increased temperature ($\geq 37.5^{\circ}\text{C}$)
 
Treatment: see endpoint 19
 
Intercurrent Event Strategy: See endpoint 11
 
Population-level Summary: See endpoint 11
	28
	
Endpoint: Parasite clearance time
 
Target Population: See endpoint 19
 
Treatment: see endpoint 19
 
Intercurrent Event Strategy: See endpoint 12
 
Population-level Summary: See endpoint 12
	29
To evaluate the safety and tolerability of the M5717-pyronaridine combination in adult and adolescent participants with acute uncomplicated malaria due to P. falciparum	
Endpoint: Incidence, severity, and seriousness of study intervention-related TEAEs, as per CTCAE v 5.0
 
Additional endpoints related to safety and tolerability up to Day 29 (± 2 days): laboratory assessments, ECGs, and vital signs.
	33

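### Read literally, the SAP's fever clearance rule can record clearance before the febrile reading that brings a participant into the analysis

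*SAP*

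**What the plan says.** **Event and time origin.** SAP 14.5: "Fever clearance time is defined as the time (in hours) from first dosing to the first measurement of temperature" below 37.5 °C "for 2 consecutive temperature readings, plus confirmed normal temperature" "24 hours after the first normal body temperature reading". The origin is first dosing for every participant.

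**Who is analysed.** SAP 14.5 removes history-of-fever entrants with no reading above 37.5 °C "at the pre-dose visit or during the 24 hours following initial dosing will not be considered for the population-level summary". SAP Section 7 puts it positively: participants above 37.5 °C "at the pre-dose visit or during the 24 hours following dosing will be included". Protocol 8.1 has the same kind of rule: entrants on history of fever with no reading above 37.5 °C "during the 24 hours following initial dosing, will not be included in this endpoint analysis". All three therefore keep a participant who is normal before dosing and first documented as febrile within the next 24 h.

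**Target population.** SAP Section 5, endpoint 28, describes "Adult and adolescent patients with acute uncomplicated malaria due to" *P. falciparum* with a temperature of 37.5 °C or above. Endpoint 11 uses the same threshold for adults in Part A.

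**Related provisions.** Inclusion criterion 4 (protocol 5.1) accepts a history of fever in the previous 24 h in place of a measured fever. SAP 14.5 also keeps participants who took fever medication before dosing. Protocol Table 2 schedules temperature before dosing and then every 6 h from 6 h.

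**The concern.** The inclusion rule looks for a fever at any time up to 24 h after dosing. The event rule looks for normal readings from dosing onward. The two are not linked: the search for clearance is not told to wait for the fever that made the participant eligible, and one normal reading 24 h later is enough to confirm it. A fever lying between the first normal reading and its confirmation is skipped.

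The same gap affects participants who are febrile before dosing. If the temperature falls, returns within 24 h and is normal at the 24 h check, the first fall counts as clearance.

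At stake are the Kaplan-Meier median fever clearance time, its interval and plot, and the Cox model in SAP 14.5. The planned groups are 12 (Part A) and 25 (Cohort B0), so a few false early events could matter.

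The inclusion threshold is a smaller point of the same kind. A reading of exactly 37.5 °C is not normal under the event definition and falls within the target population, but it does not satisfy the inclusion wording.

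**Working it through.** The documents give no expected fever clearance time, so there is no figure to reproduce. The check applies the stated rule to the schedule.

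**Inputs.** Readings at 6, 12, 18, 24 h and so on, every 6 h (protocol Table 2). The temperature entry at 72 h is unclear in the text available, but none of the cases below needs it. Normal means below 37.5 °C (SAP 14.5).

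**Rule as written.** Clearance time is the smallest post-dose *t* such that the readings at *t*, at the next scheduled time and at *t* + 24 h are all normal.

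**Amended rule.** Search only from the first febrile reading, and require every scheduled reading from *t* to *t* + 24 h to be normal. Time is still counted from dosing.

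All cases are normal before dosing, with one febrile episode:

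| Febrile readings (h) | Normal again (h) | As written (h) | Amended (h) | Difference (h) |
|---|---|---|---|---|
| 18 | 24 | 6 (6, 12, 30 normal) | 24 | 18 |
| 18, 24 | 30 | 6 (6, 12, 30 normal) | 30 | 24 |
| 18, 24, 30 | 36 | 36 | 36 | 0 |
| 24 | 30 | 6 (6, 12, 30 normal) | 30 | 24 |
| 24, 30 | 36 | 12 (12, 18, 36 normal) | 36 | 24 |
| 24, 30, 36 | 42 | 42 | 42 | 0 |

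For a first febrile reading at 6 or 12 h there are not two consecutive normal post-dose readings beforehand, so the two rules agree.

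**If the pre-dose reading may itself be the first normal reading.** The text does not settle this. If it may, a participant normal before dosing and at 6 h, first febrile at 12 h and normal at 24 h would be recorded as cleared at 0 h.

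**Direction.** Any time that satisfies the amended rule also satisfies the rule as written. The rule as written therefore returns the same time or an earlier one, never a later one.

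**How many patterns.** With 12 readings from 6 to 72 h (assuming one at 72 h), a normal pre-dose reading and at least one febrile reading at 6 to 24 h, there are 2^12 − 2^8 = 3,840 febrile/normal patterns. Clearance precedes the first fever in:
- first fever at 18 h with 30 h normal: 2^8 = 256;
- first fever at 24 h with 30 h normal: 2^7 = 128;
- first fever at 24 h with 30 h febrile and 36 h normal: 2^6 = 64.

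The total is 448. If every reading over the 24 h must be normal, the count is 0. These patterns are not weighted by likelihood, so 448 of 3,840 is not an estimate of frequency.

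**Participants febrile before dosing.** Take febrile pre-dose, normal at 6 and 12 h, febrile at 18 h and normal from 24 h. The rule as written gives 6 h. Moving only the start of the search still gives 6 h, because the first fever is the pre-dose one. Requiring all readings over the 24 h to be normal gives 24 h. Changing the start of the search is therefore not enough.

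**The case against.** The strongest reply is that a confirmed normal temperature 24 h later was meant as normal temperature maintained for 24 h. Under that reading no pattern yields clearance before the first fever. The intention is plausible, but the text does not state it. SAP 14.6, on parasite clearance, does require readings after the first zero to stay at zero over its confirmation interval. SAP 14.5 has no such wording, and a programmer following it would check one reading.

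A second reply is that censoring at fever medication would catch these cases. It does not do so reliably. It applies to medication given as continuous treatment, from the time of intake. Medication started for a fever at 18 or 24 h would come after an event already recorded at 6 or 12 h. SAP 14.5 says what happens when clearance has already been observed only for discontinuation and death.

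Three stronger readings are not supported:
- A reader might infer that clearance is recorded before the illness fever began at all. Inclusion criterion 4 requires measured or reported fever before dosing, so the point concerns the documented reading that qualifies the participant.
- A reader might infer that everyone afebrile at dosing gets a wrong value. Under the post-dose search, only late first readings with quick resolution are affected among single episodes.
- A reader might take the two wrong rows of three at each onset time in the table as a rate of two-thirds. That would need fever durations of 6, 12 and 18 h to be equally likely, and nothing in the documents supports this.

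It also stands that little depends on this endpoint. It is secondary, Cohorts B1 to B3 were not enrolled, the log-rank comparisons were dropped (SAP Section 7), and PCR-adjusted ACPR is untouched.

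**Conclusion.** The point holds as a defect of wording with a definite direction. Taken literally, SAP 14.5 can date clearance before the febrile reading that qualifies the participant. Among single episodes on the 6-hourly schedule this happens when fever is first documented at 18 h and gone by 30 h, or first documented at 24 h and gone by 36 h. The recorded time is then 6 or 12 h instead of 24 to 36 h, which is 18 or 24 h too short. The single-reading confirmation also lets a fever that returns within 24 h count as cleared in participants febrile before dosing.

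This rests on the literal text, the scheduled readings, and a search over post-dose readings only. The net effect on the Kaplan-Meier median cannot be computed, because the number of participants afebrile at dosing is not given. The endpoint is secondary and descriptive, so this is a minor correction, but one worth making. The threshold mismatch is real and affects only readings of exactly 37.5 °C.

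**What to change.** In SAP 14.5:

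- Start the search for the first normal reading at the first documented temperature of 37.5 °C or above, whether pre-dose or within 24 h after dosing. Keep first dosing as time zero.
- Require all scheduled readings from the first normal reading through its 24 h confirmation to be below 37.5 °C.
- Use 37.5 °C or above for inclusion, here and in SAP Section 7, to match the target population in SAP Section 5 (endpoints 11 and 28).

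Both changes to the rule are needed. The second covers fevers that return, including those in participants febrile before dosing. The first ties the event to the qualifying fever even if that fever is documented at an extra reading between scheduled times, which protocol Table 2 allows.

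The cost is a few sentences and a small change to the derivation code, with no new data. The downside is small: some clearance times become longer. Under SAP Section 4 the change goes in the modification history if made before data review. After data review it is labelled as a later change and documented in the clinical study report.
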